Version: 4.0

CCI

CONFIDENTIAL

Page 79 of 88

GALDERMA

(S/N: 1581)

Title

43USCH2208, Clinical Investigation Plan R Lyft Chin US

Doc id

MA-52558

Effective date: 2023-05-24 22:48

Effective

Version: 4.0

CCI

CONFIDENTIAL

Page 80 of 88

GALDERMA

6301135801

Title

43USCH2208, Clinical Investigation Plan R Lyft Chin US

Doc id

MA-52558

Effective date: 2023-05-24 22:48

Effective

Version: 4.0

CCI

CONFIDENTIAL

Page 81 of 88

GALDERMA

(S/N: 1581)

Title

43USCH2208, Clinical Investigation Plan R Lyft Chin US

Doc id

MA-52558

Effective date: 2023-05-24 22:48

Effective

Version: 4.0

CONFIDENTIAL

Page 82 of 88

GALDERMA

(S/N: 1581)

Title

43USCH2208, Clinical Investigation Plan R Lyft Chin US

[figure not shown]
Doc id

MA-52558

Effective date: 2023-05-24 22:48

Effective

Version: 4.0

CONFIDENTIAL

## 1 List of Abbreviations and Definition of Terms

| Abbreviation | Description                                    |
|--------------|--|
| AE           | Adverse Event                                  |
| AESI         | Adverse Event of Special Interest              |
| AIC          | Akaike Information Criterion                   |
| ATC          | Anatomical Therapeutic Chemical                |
| ATC-3        | Anatomical Therapeutic Chemical 3rd level      |
| ATC-4        | Anatomical Therapeutic Chemical 4th level      |
| BE           | Blinded Evaluator                              |
| BOCF         | Baseline Observation Carried Forward           |
| CDISC        | Clinical Data Interchange Standards Consortium |
| CI           | Confidence Interval                            |
| CTN          | Clinical Trial Number                          |
| EOS          | End of Study                                   |
| eCRF         | Electronic Case Report Form                    |
| FSFV         | First Subject First Visit                      |
| FST          | Fitzpatrick Skin Type                          |
| CCI          |  |
| GCRS         | Galderma Chin Retrusion Scale                  |
| ICF          | Informed Consent Form                          |
| ICH          | International Conference on Harmonization      |
| CCI          |  |
| IRB          | Institutional Review Board                     |
| CCI          |  |
| ITT          | Intention-to-Treat                             |
| KM           | Kaplan-Meier                                   |
| KR           | Kenward-Rodger                                 |
| LS           | Least Squares                                  |
| LSLV         | Last Subject Last Visit                        |
| MAR          | Missing at Random                              |
| MCMC         | Markov Chain Monte Carlo                       |
| MedDRA       | Medical Dictionary for Regulatory Activities   |
| MI           | Multiple Imputation                            |
| ML           | Maximum Likelihood                             |
| NPS          | Numeric Pain Scale                             |
| OC           | Observed Cases                                 |
| PRO          | Patient-Reported Outcome                       |
| PP           | Per-Protocol                                   |
| PT           | Preferred Term                                 |
| SAE          | Serious Adverse Event                          |
| SAP          | Statistical Analysis Plan                      |
| SD           | Standard Deviation                             |
| SOC          | System Organ Class                             |
| CCI          |  |

Confidential

Statistical Analysis Plan Version #1.0

Page 7 of 63

Effective

Version: 1.0

GALDERMA

Title  
**43USCH2208 Statistical Analysis Plan (SAP)**

Doc id  
**MA-60980**

Galderma

Protocol number: 43USCH2208

Protocol V4.0

| Abbreviation | Description                         |
|--------------|-------------------------------------|
| TI           | Treating Investigator               |
| UADE         | Unanticipated Adverse Device Effect |
| VA           | Visual Acuity                       |
| WHO          | World Health Organization           |

Effective date: 2024-05-29 18:37

Effective

Version: 1.0

Effective date: 2024-05-29 18:37

Effective

Version: 1.0

Galderma

Protocol number: 43USCH2208

Protocol V4.0

## 2 Introduction

This statistical analysis plan (SAP) describes the effectiveness and safety summaries and analyses that will be performed for Clinical Trial Number (CTN) 43USCH2208, *A randomized, evaluator-blinded, parallel group, comparator-controlled, multicenter study to evaluate the safety and effectiveness of Restylane Lyft with Lidocaine for augmentation of the chin region to improve the chin profile* and is based on the study protocol Version 4.0 dated 24MAY2023 and electronic Case Report Form (eCRF) Version 4.03 dated 14FEB2024.

## 3 Study Objectives and Overall Design

### 3.1 Study Objectives and Endpoints

#### 3.1.1 Primary Effectiveness Objective and Endpoint

The primary objective of the study is to demonstrate non-inferiority of Restylane Lyft with Lidocaine versus Juvéderm® Voluma™ XC for augmentation of the chin region to improve the chin profile by comparing change from baseline in the Blinded Evaluator live assessment of the Galderma Chin Retrusion Scale (GCRS) at 3 months after last treatment.

#### 3.1.2 Secondary Effectiveness Objective and Endpoints

The secondary objective is to evaluate the effectiveness of Restylane Lyft with Lidocaine versus a comparator-control for augmentation of the chin region to improve the chin profile.

This objective will be based on the following endpoints:

1. Responder rate based on the Blinded Evaluators' (BE) live assessment using the GCRS at 3, 6, 9 and 12 months after last treatment.

A responder is defined as a subject with at least 1 grade improvement from Baseline on the GCRS.

[figure not shown]

Effective date: 2024-05-29 18:37

Galderma

Protocol number: 43USCH2208

Protocol V4.0

### 3.2 Overall Design

This is a prospective, randomized, evaluator-blinded, parallel group, comparator-controlled, multicenter study in the US to evaluate the safety and effectiveness of Restylane Lyft with Lidocaine for augmentation of the chin region to improve the chin profile. The chin region is comprised of the anatomical areas of the pogonion, menton, and pre-jowl sulcus. Before the study starts, a randomization list will be prepared under the supervision of a designated biostatistician from the Sponsor.

Injection technique is at the Treating Investigator's discretion with needle only or a combination of needle and cannula. Restylane Lyft with Lidocaine and the comparator-

Version: 1.0

Effective

Galderma

Protocol number: 43USCH2208

Protocol V4.0

control will be administered by needle in the pogonion. The mentum and pre-jowl sulci may be injected by needle or cannula.

At least 35 subjects will be Fitzpatrick skin type (FST) IV through VI, this includes at least 18 subjects with FST V – VI, where at least 9 subjects will be FST V and at least 9 subjects will be FST VI.

After providing informed consent, eligible subjects randomized to receive either Restylane Lyft with Lidocaine or a comparator-control will be injected by the Treating Investigator at Baseline (Day 1). A follow-up telephone call should be made 72 hours after treatment and a follow-up visit should be scheduled after 14 days.

Optional touch-up treatment may be administered 1 month (4 weeks) after initial treatment, if deemed necessary by the Treating Investigator and the subject to obtain optimal aesthetic improvement. If optional touch-up is performed, a 72-hour follow-up telephone call, a follow-up visit at 14 days, and a follow-up visit at 1 month should be scheduled.

Appropriate injection volume for the chin area will be determined by the Treating Investigator but is not to exceed a maximum total volume of 4.0 mL for initial and touch-up treatments combined. Injection in the pogonion is only permitted with a needle. Both needle and cannula are permitted for injection in the other treatment areas.

Investigator blinding will be accomplished by using a Treating Investigator to administer the treatments and a Blinded Evaluator, to whom randomization and treatment are concealed, to conduct the blinded assessments. Safety assessments will be performed by non-blinded personnel.

Effectiveness and safety data will be collected for up to 12 months (48 weeks) after last treatment including physical follow-up visits at 1, 3, 6, 9 and 12 months as well as 14 days after each treatment. A subject will be involved in the study for up to 14 months, including a 21-day screening period.

### 3.2.1 Randomization Methodology

Approximately 174 subjects will be randomized (2:1) to treatment with either Restylane Lyft with Lidocaine (Treatment Group) or Juvéderm® Voluma™ XC (Control Group).

Before starting the study, a computer-generated randomization list will be prepared under the supervision of a designated biostatistician from the Sponsor. The randomization will be stratified by FST (I-III, IV or V-VI). Subjects in the FST I-III stratum will be further stratified by study site; subjects in the FST IV, or FST V-VI strata will not be further stratified by study site due to the smaller sample size in these groups.

Randomization will be performed using an Interactive Response System by assigning each subject to treatment with Restylane Lyft with Lidocaine or Juvéderm Voluma XC

Galderma

Protocol number: 43USCH2208

Protocol V4.0

according to the randomization list. Randomization numbers will be allocated in ascending sequential order to each subject.

### 3.2.2 Study Subjects

A total of 174 adult male and female subjects over the age of 21 years with the intent to undergo treatment for augmentation of the chin region, is planned to be included in this study.

To minimize potential bias in the study results, 35 subjects will be the maximum allowed to be enrolled at any one study site.

### 3.2.3 Sample Size Justification

Approximately 174 subjects will be treated in the study, randomized in a 2:1 ratio (116 with Restylane Lyft with Lidocaine: 58 with Juvéderm Voluma XC).

For sample size calculation of 174, it was assumed that the true effectiveness of Restylane Lyft with Lidocaine compared to control treatment assessed by the GCRS is approximately 0.1 point lower. A common standard deviation of 0.7 point was assumed for the treatments. Based on the non-inferiority margin of 0.5, a total sample size of 147 evaluable subjects is then required to show non-inferiority of Restylane Lyft with Lidocaine to the control treatment with a power of 90%, using a two-sided 95% CI for the difference between treatment means.

The GCRS scale is designed so that a complete scale step considers a meaningful clinical difference. A change of up to 0.5 points is not considered clinically important, thus, the non-inferiority margin of 0.5 is chosen. We have estimated the standard deviation from previous studies where the scale GCRS has been used.

Accounting for approximately 15% dropouts and non-evaluable subjects due to protocol deviations at 3 months, a total of approximately 174 subjects will be randomized in the study.

### 3.2.4 Effectiveness Assessments

#### 3.2.4.1 Galderma Chin Retrusion Scale (GCRS)

The GCRS is a validated 4 grade scale for assessment of Chin retrusion as described in Table 1 and detailed in [Section 16.3.1](#). Each score in the GCRS is exemplified by photographic images of the scale. The Blinded Evaluator and Treating Investigator will perform a live assessment of the subject's chin separately. The Blinded Evaluator will assess the GCRS at Screening, Baseline and 3, 6, 9 and 12 months after last treatment. The Treating Investigator will assess the GCRS at Screening, Baseline and 1 month after initial treatment. On visits where a treatment is performed, assessments will be done prior to any planned treatment.

Galderma

Protocol number: 43USCH2208

Protocol V4.0

**Table 1: Galderma Chin Retrusion Scale (GCRS)**

| Score | Description  |
|-------|--|
| 0     | No Retrusion: The most anterior portion of the chin is at or near a vertical line drawn from the vermillion border of the lower lip.   |
| 1     | Mild Retrusion: The most anterior portion of the chin is clearly recessed, but less than midway, between vertical lines drawn from the vermillion border of the lower lip and the oral commissure. |
| 2     | Moderate Retrusion: The most anterior portion of the chin is recessed approximately midway between vertical lines drawn from the vermillion border of the lower lip and the oral commissure.       |
| 3     | Severe Retrusion: The most anterior portion of the chin is clearly posterior to the midway point between vertical lines drawn from the vermillion border of the lower lip and the oral commissure. |

A responder indicator will be created to identify subjects that achieved at least 1 grade improvement from Baseline, on the Blinded Evaluator GCRS at a given post-Baseline visit.

GALDERMA

Title  
43USCH2208 Statistical Analysis Plan (SAP)

Doc id  
MA-60980

Effective date: 2024-05-29 18:37

Galderma

Protocol number: 43USCH2208

Protocol V4.0

Effective

Version: 1.0

Confidential

Statistical Analysis Plan Version #1.0

Page 14 of 63

GALDERMA

Title  
43USCH2208 Statistical Analysis Plan (SAP)

Doc id  
MA-60980

Effective date: 2024-05-29 18:37

Galderma

Protocol number: 43USCH2208

Protocol V4.0

Effective

Version: 1.0

Confidential

Statistical Analysis Plan Version #1.0

Page 15 of 63

GALDERMA

(S/N: 1581)

Title

43USCH2208 Statistical Analysis Plan (SAP)

Doc id

MA-60980

Effective date: 2024-05-29 18:37

Galderma

Protocol number: 43USCH2208

Protocol V4.0

*Effective*

Version: 1.0

Confidential

Statistical Analysis Plan Version #1.0

Page 16 of 63

Effective date: 2024-05-29 18:37

Galderma

Protocol number: 43USCH2208

Protocol V4.0

**3.2.4.9 Returning to Social Engagement**

A follow-up telephone call should be made 72 hours after each treatment, where the treated subject will be asked when (in hours after treatment) s/he felt comfortable returning to social engagement, such as returning to the office or other public workplace, having dinner in a public restaurant, attending a social event/gathering such as a dinner party, etc. cc

[figure not shown]
For each subject, time, in hours, until the subject feels comfortable returning to social engagement will be computed. A separate flag for each treatment will be created to determine the time in hours at which the subject responded they felt comfortable returning to social engagement. Time, in hours, until the subject feels comfortable returning to social engagement will be calculated as follows:

$$\text{Number of hours until subject feels comfortable returning to social engagement} = \text{Date and Hour of Response Flag} - \text{Date and Hour of Treatment}$$

Subjects who never feel comfortable returning to social engagement will be censored at 23:59 on the date of their telephone call visit (Visit 2a for initial treatment, Visit 3a for optional touch-up treatment). Subjects who felt comfortable returning to social engagement, but who provided a date, and no time will be censored at 23:59 on the date provided. Subjects who felt comfortable returning to social engagement, but who provided a time, and no date will be censored at the provided time on the date of their telephone call visit. Subjects who felt comfortable returning to social engagement, but who did not provide a date and time will be censored at 23:59 on the date of their telephone call visit. Subjects who never respond to the 72-hour phone call will be censored at 23:59 on the target date of their telephone call visit. Subjects dropping out before feeling comfortable returning to social engagement will also be censored at 23:59 on the target date of their telephone call visit or date of withdrawal, whichever comes first. The target date can be calculated by taking the date of treatment + 72 hours.

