8.3 Follow-up visits

8.3.1 Telephone call/Visit 2

The following should be completed at the telephone contact 72 hours (± 24 hours) after the Baseline/Initial treatment/Day 1 visit (Table 1):

Effective date: 2023-05-24 22:48

- Interview the subject regarding the Subject Diary completion and reported events since receiving treatment. Remind subject to complete the Subject Diary daily and bring it to the next on-site visit.
- Interview the subject regarding any concomitant therapies.
- Interview the subject regarding any AEs that have occurred since receiving treatment. If AEs are reported, notify the Investigator immediately and determine whether subject should return to the study center for an unscheduled visit. The Investigator should assess all reported AEs in a timely manner.
- Interview the subject regarding when (in hours after treatment) the subject felt comfortable returning to social engagements (public/social appearances) exemplified as returning to business office or other public workplace, having dinner in a public restaurant, attending a social event/gathering such as dinner party, etc.
- Remind the subject of the next scheduled on-site visit (Visit 2a), 14 days (2 weeks; +7 days) after the baseline visit (Visit 1b).

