**Table 6: AVISIT and VISIT Values**

| Visit (VISIT)  | Presentation in Tables (AVISIT)            | Presentation in Listings |
|--|--|--------------------------|
| Visit 1a Screening Day -21 to Day 1                            | Visit 1a (Screening) {or Baseline}         | Visit 1a                 |
| Visit 1b Baseline/Tx Day 1                                     | Visit 1b (Baseline) {or Baseline}          | Visit 1b                 |
| Visit 2 (TC) 72 hrs after Baseline (+/- 24 hrs)                | Visit 2 (Hour 72 after Treatment)          | Visit 2                  |
| Visit 2a 14 days after Baseline (+ 7 days)                     | Visit 2a (Day 14 after Treatment)          | Visit 2a                 |
| Visit 3 1 month after Baseline (+ 7 days)                      | Visit 3 (Month 1 after Treatment)          | Visit 3                  |
| Visit 3a (TC) 72 hrs after Optional Touch Up (+/- 24 hrs)      | Visit 3a (Hour 72 after Optional Touch-up) | Visit 3a                 |
| Visit 3b 14 days after Optional Touch Up (+ 7 days)            | Visit 3b (Day 14 after Optional Touch-up)  | Visit 3b                 |
| Visit 3c 1 month after Optional Touch Up (+ 7 days)            | Visit 3c (Month 1 after Optional Touch-up) | Visit 3c                 |
| Visit 4 Follow-up 3 Months after Last Treatment (+/- 14 days)  | Visit 4 (Month 3 after Last Treatment)     | Visit 4                  |
| Visit 5 Follow-up 6 Months after Last Treatment (+/- 14 days)  | Visit 5 (Month 6 after Last Treatment)     | Visit 5                  |
| Visit 6 Follow-up 9 Months after Last Treatment (+/- 14 days)  | Visit 6 (Month 9 after Last Treatment)     | Visit 6                  |
| Visit 7 Follow-up 12 Months after Last Treatment (+/- 14 days) | Visit 7 (Month 12 after Last Treatment)    | Visit 7                  |

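### SAP 3.2.4.9 right-censors subjects who did return to social engagement if their date or time is incomplete, which overstates time to return; the same paragraph misnames the telephone call visit.

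*SAP*

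**What the plan says.** SAP 3.2.4.9 computes hours to return as the date and hour of the response minus the date and hour of treatment. Three of its rules concern subjects who did feel comfortable returning but whose answer is incomplete:

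- Date without time: "but who provided a date, and no time will be censored at 23:59 on the date provided".
- Time without date: "but who provided a time, and no date will be censored at the provided time on the date of their telephone call visit".
- Neither: "but who did not provide a date and time will be censored at 23:59 on the date of their telephone call visit".

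The paragraph uses the same word, censored, for subjects who never felt comfortable, never answered the call or dropped out. It gives no event indicator that separates these groups from the returners.

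The paragraph also identifies the "telephone call visit (Visit 2a for initial treatment, Visit 3a for optional touch-up treatment"). SAP Table 6 lists "Visit 2 (TC) 72 hrs after Baseline (+/- 24 hrs") and, as a different visit, "Visit 2a 14 days after Baseline (+ 7 days"). Its touch-up entry is "Visit 3a (TC) 72 hrs after Optional Touch Up (+/- 24 hrs"), so Visit 3a is right. Protocol 8.3.1, for Visit 2, agrees with Table 6: "The following should be completed at the telephone contact 72 hours (± 24 hours) after the Baseline/Initial treatment/Day 1 visit". Protocol 8.3.2 makes Visit 2a the 14-day follow-up visit.

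**The concern.** Right-censoring states that the event had not yet occurred at the censoring time. These subjects have reported the opposite. A missing hour or date is a loss of precision about when the event happened, and it is bounded by the reported date or by the call. Coding it as a non-event removes returns from the numerator while the subject stays in the risk set until the censoring time, so the curve sits too high. For a recovery-time endpoint the curve and the median are the reported result.

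The visit label is a second, separate fault. Read literally, it would move the censoring date of subjects who had not returned from the 72-hour call to the 14-day visit.

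**Working it through.** The plan states no rate, event count or power for this endpoint, so there is no figure of its own to reproduce. The check has four steps.

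**1. Direction and rough size by hand.** Let S(t) be the true share not yet returned at t, and let a fraction m of returners, unrelated to their return time, be censored at the moment they return. The event hazard is then multiplied by (1 − m), so Kaplan-Meier estimates S(t)^(1−m), which exceeds S(t) wherever S(t) lies between 0 and 1. The estimated median is the time at which the true S equals 0.5^(1/(1−m)).

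Assume lognormal times with median 24 h and log-SD 0.9 (neither is in the documents). The true share not returned at 72 h is 1 − Φ(ln(72/24)/0.9) = 1 − Φ(1.221) = 0.111.

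- m = 5%: 0.5^(1/0.95) = 0.482, median 25.0 h; 0.111^0.95 = 0.124.
- m = 20%: 0.5^(1/0.8) = 0.420, median 28.8 h; 0.111^0.8 = 0.172.
- m = 40%: 0.5^(1/0.6) = 0.315, median 37.0 h; 0.111^0.6 = 0.268.

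The plan's rule does worse than this, because it censors at 23:59 and so keeps each such subject at risk for longer.

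**2. The plan's rule, simulated.** The setting is the same lognormal, the call uniform over 72 ± 24 = 48 to 96 h, treatment between 09:00 and 17:00 (assumed), incomplete answers all date-only, and non-returners censored at 23:59 on the call date. Each cell gives the median and the share not returned at 72 h. The truth is 24 h and 11%.

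| Date-only share of returners | Plan (censored) | Event at 23:59 | Interval-censored within the date |
|---|---|---|---|
| 5% | 25 h, 14% | 25 h, 12–13% | 24 h, 11% |
| 20% | 31 h, 22% | 29 h, 13% | 24 h, 11% |
| 40% | 43 h, 34% | 33 h, 13% | 24 h, 11% |

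With no incomplete answers the plan still gives about 12% at 72 h, because subjects who had not returned are carried to 23:59 on the call date. About 1 point of each 72-hour excess in the plan column therefore has that cause.

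**3. A different shape.** With exponential times, a true median of 24 h and a mix of incomplete answers (60% date only, 20% time only, 20% neither), the plan gives 25.7, 32.7 and 74.5 h at 5%, 20% and 50% incomplete. Interval censoring gives 24 to 25 h on a 1-hour grid. With a true median of 12 h the plan gives 12.9, 16.5 and 38.8 h; with 48 h it gives 51.7 h, 66.6 h and a median not reached. The direction is the same in all nine scenarios.

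**4. The visit label alone.** Literal use of Visit 2a moves censoring from 48–96 h to 14 × 24 = 336 h up to 21 × 24 = 504 h. In the lognormal setting the median does not change at any rate tried, and the share not returned at 72 h rises by 1 to 2 points. In the exponential setting with no incomplete answers that share goes from 0.141 to 0.154. The median moves only where the estimate already lies beyond 48 h, the earliest call: for example, from 74.5 h to 79.7–82.6 h at 50% incomplete.

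**The case against.** Several points on the other side stand.

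- A reader might infer that all returners are censored. They are not: those who give both a date and a time remain events. The question is asked by staff in an interview, and Protocol 10.4.2 describes eCRF checks and queries, so the incomplete share may be small. At 5% the median moves by about 1 h.
- A reader might infer that the Visit 2a label drives the overstatement. Step 4 shows that it hardly matters. The paragraph itself speaks of the telephone call and sets a target date of treatment plus 72 hours, so this looks like a slip in a label.
- Counting these subjects as events at 23:59 leaves much of the shift in the median. At 20% it gives about 29 h against a true 24 h, so the choice of replacement rule matters.
- The analysis section for this endpoint is blacked out. Kaplan-Meier appears only in the SAP's abbreviation list.
- The rules are identical in both arms, and SAP 9.2 gives p-values outside the primary endpoint only as an aid to interpretation. A biased comparison would need incomplete answers or return times to differ by arm, and nothing in the documents shows this.

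It could also be said that censored is used loosely here to mean imputed. The text does not support that reading, since the same word covers subjects who had not returned. If it was meant, the wording still needs to change.

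**Conclusion.** The rule is wrong as written for returners with an incomplete date or time: known events become non-events, and in a time-to-event analysis time to return is overstated. The effect is about 1 h on a 24 h median at 5% incomplete, 7 h at 20% and 19 h at 40%, under the lognormal, date-only assumptions above. The true share of incomplete answers is not in the documents, and the use of Kaplan-Meier is inferred.

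The documents do not support extending this to a biased treatment comparison or to the GCRS non-inferiority result. The Visit 2a label contradicts SAP Table 6 and Protocol 8.3.1 and 8.3.2 and should be corrected, but as a matter of consistency.

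**What to change.** Rewrite the censoring rules in SAP 3.2.4.9 with an explicit event indicator:

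- Returner with date and time: event at that time.
- Returner with date only: event, interval-censored within that date (and no later than the call).
- Returner with no date, with or without a clock time: event, interval-censored between treatment and the call.
- Right-censoring only for subjects who had not returned by the call, were not reached, or withdrew.

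Estimate the curve with an interval-censored (Turnbull) estimator. If a plain Kaplan-Meier curve is preferred, an event at 23:59 is simpler but cruder and still overstates the median; the SAP should say so. Report the number of incomplete answers by arm.

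Change Visit 2a to Visit 2 for the call after initial treatment.

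The cost is one paragraph and one derivation. No new data are needed and no subject is lost from the analysis.
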